5.1.9 Handling Analysis of Placebo Switching Subjects

As described in the randomization section above (Section 5.1.7), subjects originally randomized to placebo may be switched to EDS-EP treatment during the extension treatment period at Visit 9

(“Month 6”) or Visit 12 (“Month 9”). This will cause re-distribution of subjects within the analysis populations. For example, the number of ITT subjects in the placebo group will decrease over the course of the study, while the number of ITT subjects in the two EDS-EP treatment groups will increase over the course of the study. Although there will be re-distribution, the total number in each population (ITT, FAS, Safety, PP) will remain consistent. Re-distribution will be presented on the subject disposition table. In order to maintain consistency, subjects who discontinue prior to a switch month, will not be dropped from the total but instead be presented in their intended treatment group. Presentation within intended treatment group is possible because randomization assignments for Visit 9 (“Month 6”) and Visit 12 (“Month 9”) (the placebo switch months) were identified at the same time as the initial randomization assignment. Because subjects who discontinue prior to Visit 9 (“Month 6”) will not have efficacy data past the point of discontinuation, the rules described above for missing data will be applicable for analysis of these subjects (e.g., Jump to Reference, LOCF, and OC) within the initial treatment period. Placebo switching subjects who do not make it to the point at which they would have switched will not appear in related post-switch analyses.

5.1.10 Hypothesis Testing and Handling of Multiple Comparisons

The high dose of the primary efficacy end point will be tested at the two-sided significance level of $\alpha \leq 0.05$. With this requirement, the overall family-wise error rate (FWER) can be no greater than $\alpha = 0.05$, two-sided. The study will be judged statistically significant if the high dose of the primary efficacy endpoint is significant.

For the primary efficacy end point, the low dose will be tested only if the high dose is found statistically significant for the primary and key secondary endpoints. In this way the 0.05 two-sided significance level will be maintained, and no adjustment will be necessary.

The null (H_0) and alternative (H_1) hypotheses are:

H_0 : there is no difference between Group 2-EDS-EP high dose and the placebo group with respect to change from baseline in mICARS

H_1 : there is a difference between Group 2-EDS-EP high dose and the placebo group with respect to change from baseline in mICARS

Statistical significance for efficacy and the study as a whole will be declared if:

The null hypothesis for the primary efficacy analysis (no statistical difference between EDS-EP high dose and placebo) with respect to change from baseline in mICARS is rejected at the 0.05 two-sided significance level.

Following the testing for the primary endpoint for the high dose, analysis of the key secondary endpoint will be performed only if the primary analysis for the high dose level was significant at the two-sided 0.05 level.

Efficacy of the EDS-EP low dose versus placebo:

If the null hypothesis for the primary efficacy analysis (no statistical difference between EDS-EP high dose and placebo) with respect to change from baseline in mICARS and the null hypothesis for the key secondary endpoint are rejected, the efficacy of EDS-EP low dose versus placebo with respect to change from baseline in mICARS will be tested at the 0.05 two-sided significance level, and testing will proceed hierarchically to the key secondary endpoint also at the 0.05 level.

The analyses for the QOL scale (EQ-5D-5L) and C-SSRS (a safety parameter) will be exploratory and will not be adjusted for multiplicity.

Further analyses will make the same comparisons at Visit 12 (“Month 9”) of treatment, and again, at Visit 15 (“Month 12”) of treatment. Because these later analyses will be underpowered, these analyses will be for descriptive purposes only and will not follow the sequential testing approach. P-values will be presented strictly as an aid to understanding the results for all comparisons but will provide no basis for statistical inference.

5.2 Subject Characteristics

5.2.1 Subject Disposition

The number and percentage of randomized subjects within each region will be summarized by treatment group and placebo switching subgroups, and regional enrollment will be compared across EDS-EP and pooled placebo treatment groups using the Pearson Chi-square test, or Fisher’s Exact test if any cell count is <5 . This summarization will be repeated by region and site, with no statistical comparisons performed.

The number of screened subjects, and the number and percentage of randomized subjects who are in the Full Analysis Set, in the Safety Set, and in the Per Protocol Set, and the number and percentage of randomized subjects excluded from the Per Protocol Set by reason for exclusion (including discontinuation due to the COVID-19 pandemic) will be summarized by initial treatment and placebo switch sub-group.

The number and percentage of randomized subjects who are ongoing in the study (at the time of the primary analysis), complete the study, who discontinue the study (overall and by primary reason for discontinuation) will be summarized by treatment group, placebo switching sub-group, and overall. This disposition will also be summarized by region.

The number and percentage of randomized subjects who discontinue the study due to COVID-19 restrictions will be summarized by treatment group, placebo switching sub-group, and overall.

6	The patient and his/her parent/caregiver (if below the age of consent), or a legal representative, has provided written informed consent to participate. If consent is provided solely by the caregiver in accordance with local regulations, the patient must provide assent to participate in the study.
Exclusion Criteria	
General	
1	Females that are 
 a. pregnant, or are breast-feeding (for EU countries only); b. of childbearing potential, pregnant, or are breast-feeding (for US and Rest of World countries). Females of childbearing potential using adequate birth control, as determined by their Health Care Provider, will be eligible.
2	A disability that may prevent the patient from completing all study requirements.
3	Current participation in another clinical study.
Medical History and Current Status	

Table 4. Inclusion and Exclusion Criteria

4	CD4+ lymphocytes count <400/mm ³ (for patients 6 years of age) or <150/mm ³ (for patients > 6 years). In presence of oral infections, like oral candidiasis, documented at the screening or recurrent as per medical history documentation, the limit increases to <200/mm ³ (for patients > 6 years).
5	Loss/removal of 250 mL or more of blood within the past 4 weeks prior to screening.
6	Current neoplastic disease or previous neoplastic disease not in remission for at least 2 years.
7	History of severe impairment of the immunological system.
8	Severe or unstable pulmonary disease.
9	Uncontrolled diabetes. Patients with diabetes that has been stabilized (i.e. no hypoglycemic or hyperglycemic episodes in the past 3 months) will be eligible.
10	Any other severe, unstable, or serious disease or condition that in the Investigator's opinion would put the patient at risk for imminent life-threatening morbidity, need for hospitalization or mortality.
11	Any clinically significant abnormality on standard laboratory examinations (hematology, biochemistry, urinalysis) at screening that remains abnormal on repeat testing. Eligibility of patients with abnormal laboratory test values will be determined by the Investigator, in consultation with the Medical Monitor.
12	Confirmed hemoglobinopathies, e.g. hemoglobin C disease, sickle cell anemia, or thalassemia.
13	Moderate or severe renal and/or hepatic impairment.
Prior/Concomitant Medication	
14	Any previous oral or parenteral steroid use within 4 weeks before Baseline. Treatment with inhaled or intranasal steroids for asthma or allergies, as well as use of topical steroids will be permitted.
15	Chronic condition or prior allergic reaction representing a contraindication to the use of dexamethasone or other steroid drugs.
16	Has participated in any other trial with an investigational drug and received a dose within 30 days or 10 half-lives (whichever is greater) from the start of the 30-day Screening Period.
17	Has participated in a previous trial with EDS.

Table 4. Inclusion and Exclusion Criteria

18	Requires any concomitant medication prohibited by the protocol.
19	Has taken a drug or treatment known to cause major organ system toxicity during the past year.
20	Use of any drug that is a strong inducer/inhibitor of CYP3A4 within 4 weeks before baseline.

5.2.3 Background and Demographic Characteristics

Descriptive summaries of subject demographic and baseline characteristics will be presented by treatment group and overall for the safety population and full analysis set according to treatment during the initial treatment period.

The following demographic data and baseline characteristics will be summarized:

- Age at randomization (years) as a continuous variable and as a categorical variable (6-9 years, ≥ 10 years);
- Sex
- Ethnicity
- Race
- ICARS total score
- Genetic characteristics
- Disease severity

Categorical age, sex, ethnicity, and race will be compared between treatment groups using the Pearson Chi-square test, or Fisher’s Exact test if any cell count is < 5 .

5.2.4 Extent of Treatment Exposure and Compliance

Unless specified otherwise, extent of exposure and compliance parameters will be summarized for the safety population by treatment received during the initial treatment period, Visits 9 to 12 (“Month 6 to 9”), and Visits 12 to 15 (“Month 9 to 12”), and by treatment scheme received (the seven schemes assigned at randomization) for the total study. Table 5 illustrates how subjects will be allocated to treatment during different periods of the study, under the assumption that no subjects drop out.

Table 5. Planned Subject Allocation to Treatment During Each Study Period

	EDS-EP Low Dose	EDS-EP High Dose	Placebo	Non- switch Placebo	Visit 9 EDS-EP Low Dose	Visit 9 EDS-EP High Dose	Visit 12 EDS-EP Low Dose	Visit 12 EDS-EP High Dose
Initial Treatment Period	60	60	60					

Visit 9 ("Month 6") to Visit 12 ("Month 9")	60	60		40	10	10		
Visit 12 ("Month 9") to Visit 15 ("Month 12")	60	60		20	10	10	10	10

Note: Table presents number of subjects allocated per treatment per period assuming no subjects drop out.

Duration of Treatment and Number of Infusions

Duration of treatment in the initial treatment period will be calculated in days as the date of the last infusion of study treatment during the initial treatment phase (Visit 9) – date of the first infusion of study treatment + 1. Duration of treatment for Visits 9 to 12 ("Month 6 to 9") will be calculated in days as the Visit 12 infusion date – the Visit 9 infusion date + 1, and the duration of treatment for Visits 12 to 15 ("Month 9 to 12") will be calculated in a similar manner. Total duration of treatment (initial treatment period + extension treatment period) will be calculated in days as the date of last infusion of study treatment – date of the first infusion of study treatment + 1.

Duration of treatment and number of infusions received will be summarized by treatment period using summary statistics for continuous variables. The number and proportion of subjects with duration of treatment longer than 228 days in the initial treatment period will be summarized. The exact loaded dose of dexamethasone in Erydex administered to each subject at each dosing visit will be summarized.

Extent of Exposure

Total monthly treatment exposure is defined as the count of monthly treatments, including missed monthly treatments, from the first monthly treatment to the last monthly treatment.

Continuous Exposure 1 (EryDel definition) is defined as monthly treatments with a maximum of a one monthly treatment interruption at any time during the study. Continuous Exposure 2 (CCI definition) is defined as monthly treatments with no missed treatments.

For each type of treatment (low dose, high dose, and placebo), separately, the number of subjects with each total monthly treatment exposure will be summarized. For each total monthly treatment exposure, the number of subjects in each of the following categories will be summarized:

- Missing ≤ 1 monthly treatment (Continuous Exposure 1)
- No missed monthly treatments (Continuous Exposure 2)
- Missing ≥ 2 non-consecutive monthly treatments
- Missing ≥ 2 consecutive monthly treatments

Dosing Compliance

Percentage treatment compliance during a given period will be calculated for all treated subjects within the period using the following formula.

$$\text{Compliance with study medication dosing (\%)} = \frac{A}{P} \times 100$$

where for the initial treatment period:

- A = Total number of injections actually administered through Visit 9 (“Month 6”)
- P = Total number of injections scheduled to receive up to Visit 9 (“Month 6”)

where for the Visits 9 to 12 (“Month 6 to 9”) period:

- A = Total number of infusions actually administered from the day after Visit 9 (“Month 6”) through the day of Visit 12 (“Month 9”)
- P = Total number of infusions scheduled to receive from the day after Visit 9 (“Month 6”) through the day of Visit 12 (“Month 9”)

where for the Visits 12 to 15 (“Month 9 to 12”) period:

- A = Total number of infusions actually administered from the day after Visit 12 (“Month 9”) through the day of Visit 15 (“Month 12”)
- P = Total number of infusions scheduled to receive from the day after Visit 12 (“Month 9”) through the day of Visit 15 (“Month 12”)

where for the total treatment period overall (initial plus extension):

- A = Total number of infusions actually administered
- P = Total number of infusions scheduled to receive up to Visit 15 (“Month 12”)

Dosing compliance will be summarized using summary statistics for continuous variables. The number and percentage of subjects completing 6 infusions within 228 days during the initial treatment period will also be summarized. Dosing compliance excluding subjects discontinued due to the COVID-19 pandemic will be also be provided.

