1.2 Study Design

This is an international (North America, Europe, Africa, Asia, and Australia), multi-center, one year, randomized, double-blind, placebo-controlled, Phase III study, designed to assess the effect of two non-overlapping dose ranges of EDS-EP, administered by IV infusion once per month, on neurological symptoms of subjects with AT. All subjects who complete the assessments as designed over the initial treatment period of the trial will be eligible to continue in an additional double-blind, placebo-controlled extension designed to collect information on the long-term safety and efficacy of the trial treatments.

The protocol planned for 180 subjects to be enrolled, and those meeting all of the inclusion/exclusion criteria were randomized to receive one of the two dose ranges of EDS-EP or placebo (1:1:1 with the intent of randomizing 60 subjects per group) as follows:

- **Group 1, Low Dose, EDS-EP low dose range of ~5-10 mg DSP/infusion:** CCI
[REDACTED]
- **Group 2, High Dose, EDS-EP high dose range of ~14-22 mg DSP/infusion:** CCI
[REDACTED]
- **Group 3, Placebo EDS infusion:** CCI
[REDACTED]

Due to the impact of COVID-19, the company decided to complete enrollment with 175 patients.

A minimization procedure was employed to ensure that the proportions of male and female, and younger (6 to <10 years) and older (≥ 10 years) subjects are comparable across the three treatment groups. Every attempt was made to ensure the same balance was achieved across different regions. In the Initial Treatment Period, each subject will receive 6 infusions of EDS-EP (low or high dose) or placebo, given at monthly intervals. Similarly, subjects entering the Extension Treatment Period will continue on the randomized treatment and will receive 6 monthly infusions of EDS-EP or placebo.

Randomization/placebo switching will take place at 3 time points, as described in [Section 5.1.7](#).

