5.4.1 Adverse Events

Adverse events (AEs) will be coded using MedDRA version 19.0. Coding will include system organ class and preferred term. All verbatim descriptions and coded terms will be listed for all AEs.

Adverse events of special interest include those which are potentially steroid related and those indicative of adrenal insufficiency. These will be summarized separately.

If the assessment of seriousness is missing for an event, then the event will be considered serious as a worst case. The same rule will be applied in case of missing relationship data (the worst relationship will be assumed) and missing severity data (severe will be assumed).

Each AE recorded on the CRF will be classified as either a pre-treatment AE or a treatment-emergent AE (TEAE). Adverse events occurring >60 days after the last dose of study drug will not be considered treatment emergent.

Pre-treatment AEs

Pre-treatment AEs will be defined as AEs that started and either stopped before the first infusion of study treatment or continued after and did not worsen in intensity during the treatment period. Any pre-treatment AEs identified will not be summarized by system organ class and preferred term but they will be flagged on all listings of AEs (all AEs and serious AEs).

Treatment-emergent AEs

Each adverse event will be classified as treatment emergent or not during one of three treatment periods:

- The initial treatment period (Period 1), defined as the day of the first infusion through the day just prior to the day of the Visit 9 (“Month 6”) infusion, or ≤60 days after last dose if the subject never continued past this period;
- The Visit 9 (“Month 6”) to Visit 12 (“Month 9”) period (Period 2), defined as the day of the Visit 9 (“Month 6”) infusion through the day just prior to the day of the Visit 12 (“Month 9”) infusion, or ≤60 days after the last dose if the subject never continued past this period; and
- The Visit 12 (“Month 9”) to Visit 15 (“Month 12”) period (Period 3), defined as the day of the Visit 12 (“Month 9”) infusion through 60 days after the last dose.

AEs starting on or after the date/time of the first infusion of a period and prior to the date/time of the first infusion of the next period will be considered TEAEs during the period, for example:

- Events that started on the day of or after the first infusion and are not a continuation of a pre-treatment event.
- Events that started before the first infusion and worsened after the first infusion.

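### SAP 5.2.4 compliance windows put infusions 7 and 10 in the period before the one they open, and two duration rules are faulty at the same visits

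*SAP*

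**What the plan says.** **Plan of infusions.** SAP 1.2 states that in the initial period "each subject will receive 6 infusions of EDS-EP (low or high dose) or placebo, given at monthly intervals", and that subjects entering the extension "will receive 6 monthly infusions of EDS-EP or placebo".

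**Compliance (SAP 5.2.4).** Compliance is A/P × 100.
- Initial period: A is "Total number of injections actually administered through Visit 9" and P is "Total number of injections scheduled to receive up to Visit 9".
- Visits 9 to 12: A is "Total number of infusions actually administered from the day after Visit 9", running through the day of Visit 12.
- Visits 12 to 15: A is "Total number of infusions actually administered from the day after Visit 12", running through the day of Visit 15.
- In both later periods P uses the same window as A.

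**Duration (SAP 5.2.4).** The initial period ends at "the last infusion of study treatment during the initial treatment phase (Visit 9"), minus the first infusion date, plus 1. The Visits 9 to 12 duration runs from the Visit 9 infusion date to the Visit 12 infusion date, plus 1. The Visits 12 to 15 duration is to follow the same pattern.

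**Grouping (SAP 5.2.4).** Per-period summaries are by treatment received in the period. Table 5 places all 60 planned placebo subjects under placebo in the initial period, and 40 under non-switch placebo in Visits 9 to 12.

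**Other period definitions.** SAP 5.4.1 gives Period 1 as "defined as the day of the first infusion through the day just prior to the day of the Visit 9" infusion, and Period 2 likewise stops the day before the Visit 12 infusion. SAP 5.2.5 uses the same boundaries for concomitant medication.

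**The concern.** Switching from placebo takes place at Visit 9 and Visit 12 before that day's infusion (protocol 11.5.1 and 11.5.3). A boundary drawn after the infusion therefore leaves the first active dose in a column headed placebo. The same section summarises subjects who complete six infusions within 228 days in the initial period, which cannot be reconciled with a window that holds seven.

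At stake is whether the per-period compliance tables (14.1.8.1 and 14.1.8.2) and the per-period durations in Table 14.1.7.1 mean what their labels say. A programmer would also have to guess the initial-period denominator and the end of the last period.

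**Working it through.** **1. Infusion map (protocol Tables 2A and 2B).** Infusions 1 to 6 are at Visits 1, 4, 5, 6, 7 and 8. Infusions 7 to 9 are at Visits 9 to 11, and 10 to 12 at Visits 12 to 14. Visit 15 has none. The planned 6 + 6 = 12 is reproduced only if the Visit 9 infusion belongs to the extension. SAP Table 1 agrees, since it names Infusion 6 as the one before Visit 9.

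**2. Infusions in each window.**

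| Period | SAP 5.2.4 compliance windows | SAP 5.4.1 boundaries |
|---|---|---|
| Initial | 1–7 (7) | 1–6 (6) |
| Visits 9 to 12 | 8–10 (3) | 7–9 (3) |
| Visits 12 to 15 | 11–12 (2) | 10–12 (3) |
| Total | 12 | 12 |

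**3. Switchers' first active doses.** A Month 6 switcher has 6 planned active infusions, of which 1 falls in the initial, placebo-labelled window: 1/6 = 17%. A Month 9 switcher has 3, of which 1 falls in the Visits 9 to 12 non-switch placebo window: 1/3 = 33%. Table 5 plans 20 switchers at each point, so 20 + 20 = 40 infusions are affected. If the 175 enrolled split evenly (an assumption), the count is 2 × 175/9 ≈ 39.

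**4. Initial-period compliance.** The SAP does not say whether P includes the Visit 9 infusion.

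| Subject | A | P = 6 | P = 7 |
|---|---|---|---|
| Continues, no dose missed | 7 | 117% | 100% |
| Continues, one dose missed | 6 | 100% | 86% |
| Takes all six, stops at Month 6 | 6 | 100% | 86% |

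Under either fixed P, the second and third rows cannot be told apart. In the two later periods A and P share a window (3/3 and 2/2), so the boundary cannot push compliance above 100%.

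**5. Duration.** The 228-day maximum in the note to SAP Table 1 is reproduced as 6 intervals × (28 + 10) days = 228, taking the 28-day upper interval and 10-day window from protocol 11.2. The SAP formula adds 1, so a subject at the maximum has 228 + 1 = 229 days and is counted as longer than 228.

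The boundary dates are counted twice. With nominal 30-day spacing, and the last period ended at the Visit 14 infusion (an assumption, because there is no Visit 15 infusion), the durations are 181 + 91 + 61 = 333 days. The total-study formula gives 330 + 1 = 331.

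**6. Check of the fix.** With the 5.4.1 boundaries a full complier scores 6/6, 3/3 and 3/3. Nominal durations become 180 + 90 + 61 = 331, which matches the total. The subject at the maximum has (228 − 1) + 1 = 228 days.

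**The case against.** The best defence is that P can be read subject by subject: 7 for those who continue, 6 for those who stop, since Table 2A shows no infusion at Visit 9 and infusion 7 appears only in the extension table. Full compliers then score 7/7 and 6/6, both 100%. That reading is reasonable, but the SAP does not state it. It also leaves infusion 7 in the initial period and infusion 10 in Visits 9 to 12.

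Stronger conclusions are tempting, and the documents do not support them:

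- *The duration rules also move the switchers' first active dose to placebo.* They do not. The Visit 9 and Visit 12 infusion dates end one period and start the next, so a switcher's active duration still includes the first active dose. The boundary day is counted twice.
- *All exposure figures are wrong for every switcher.* Total monthly exposure is counted separately by type of treatment, the seven-scheme summaries cover the whole study, and loaded dose is given by visit. None of these uses the compliance windows. The number of infusions is summarised by period, but the SAP does not apply those windows to it.
- *Compliance exceeds 100% throughout.* This can follow from the boundary only in the initial period, and only if P = 6.
- *Exposure and adverse-event tables cannot be used together.* SAP 5.4.1 uses subjects treated in the period as the denominator and plans no exposure-adjusted rates, so no planned analysis fails for this reason.

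It is also fair to say that ending the initial duration near Visit 9 suits the 228-day threshold. Ending it at Visit 8 would not: the maximum would be about 5 × 38 = 190 days, and the count above 228 would lose its meaning.

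**Conclusion.** The compliance rule is wrong as written. Its windows hold 7/3/2 infusions against a plan of 6/3/3, contradict the SAP's own boundaries in 5.2.5 and 5.4.1, and place about 40 planned first active doses in placebo-labelled periods. The infusion counts follow from the visit tables and need no assumption. The percentages in the initial period depend on how P is read: 117% for a full complier who continues and a hidden missed dose if P = 6, or 86% for a six-dose completer who stops if P = 7 for everyone.

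Two duration faults stand as well: the Visits 12 to 15 rule has no end date, and a subject exactly at the 228-day limit is reported as over it.

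The effect is confined to descriptive per-period compliance and duration tables. The primary efficacy analysis, Per Protocol membership (which has its own rule in SAP section 2) and the total-study scheme summaries are not affected. The change is still worth making because the tables would otherwise be wrong or rest on a programmer's guess.

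**What to change.** In SAP 5.2.4:

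1. Start each period on the day of the Visit 9 or Visit 12 infusion, as in 5.4.1, and say that this also applies to the per-period number of infusions.
2. Set P to 6 (Visits 1 to 8), 3 (Visits 9 to 11) and 3 (Visits 12 to 14), with A counted over the same visits.
3. End the initial-period duration on the day before the Visit 9 infusion. For subjects who do not continue, use the Visit 9 assessment date without adding 1. Do not end it at Visit 8, so that the 228-day threshold still applies.
4. End the Visits 9 to 12 duration on the day before the Visit 12 infusion, and the last period at the last infusion given.

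The cost is SAP wording and program logic. No data collection, hypothesis test or analysis set changes.
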